8.11.1 ADVERSE EVENTS

All AEs will be summarized among the safety population by frequency per treatment arm. These frequencies will be presented overall and separately by dose, and will depict overall, by system organ class and by preferred term, the percentage of subjects affected. Additional frequencies will be presented with respect to maximum severity and to strongest relationship to Study Treatment. Multiple occurrences of the same AE will be counted only once following a worst-case approach with respect to severity and relationship to Study Treatment. All serious AEs will also be summarized as above.

The main summary of safety data will be based on events occurring within 28 days of any dose. For this summary, the frequency of preferred term events will be compared between study arms with risk differences and 95% confidence intervals, using the method of Miettinen and Nurminen [29]. As this analysis will use many event categories, and produce many confidence intervals, caution should be exercised when interpreting these confidence intervals. Separate summaries will be based on events occurring within 7 days of any dose and regardless of when they occurred.

For AE data, partial start dates will be imputed to the date of treatment to conservatively report the event as treatment-emergent, whenever the portion of the date is consistent with that of the study treatment. Otherwise, it will be imputed to the earliest date consistent with the partial date. A completely missing onset date will be imputed as the day of treatment. Partial stop dates will be assumed to be the latest possible day consistent with the partial date.

AE duration will be calculated as (Stop Date – Start Date) + 1.

8.12 VITAL SIGNS

Measurements for vital signs as well as changes from baseline will be summarized with descriptive statistics: mean standard deviation, minimum, median, and maximum values by time point and treatment arm, for the Safety population. Baseline is defined as the last measurement prior to the first treatment administration.

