7.1.9 PROCEDURES FOR DOCUMENTING PREGNANCY DURING STUDY

Subjects who are pregnant or expect to become pregnant during the course of the study up to Week 36 will be excluded from participation in the study. Should a subject become pregnant after receiving the first study treatment in the study, she will not be given any further study treatments. A Pregnancy Form will be completed by the site personnel and submitted to the sponsor or its designee within 24 hours after learning of the pregnancy. Site personnel will submit the Pregnancy Form to the Sponsor or its designee by fax, as described in Section 7.4.2.

The investigator will also report this event to the IRB within 24 hours of becoming aware of the pregnancy. Sites must request the subject's permission to query pregnancy outcome and follow each subject to determine the outcome of the pregnancy. Results will be summarized in the clinical study report (CSR).

Subjects who become pregnant at any point during the study will continue to be followed for safety assessments without receiving further study treatment. Procedures that are contraindicated during pregnancy, including additional treatments, must not be performed. Investigators should use clinical judgment regarding subsequent study-related blood collection based on the presence or absence of anemia in each subject.

All pregnancies that occur from the time of first study treatment through the follow up visits must be reported. The investigator will monitor the subject and follow the outcome of the pregnancy. If the end of the pregnancy occurs after the study has been completed, the outcome will be reported directly to the study team and the medical monitor.

7.2 METHODS AND TIMING OF THE COLLECTION AND RECORDING OF SAFETY DATA

Non-serious AEs and SAEs (and UADEs) will be collected for each subject from the time when informed consent is obtained through Week 88.

The sources of AEs cover:

- 1. The subject's response to questions about her health (a standard non-leading question such as 'How have you been feeling since your last visit?' is asked at each visit).
- 2. Symptoms spontaneously reported by the subject.
- 3. Evaluations and examinations where the findings are assessed by the investigator to be clinically significant changes or abnormalities.
- 4. Other information relating to the subject's health becoming known to the investigator (e.g. hospitalization).

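### The adverse-event onset rule does not check the stop date, so an event that ended before Dose 1 can be counted as treatment-emergent with a zero or negative duration (minor)

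*Protocol*

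**What the plan says.** All references are to the protocol, version 5.0.

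- **Partial onset (section 8.11.1).** The rule is that "partial start dates will be imputed to the date of treatment to conservatively report the event as treatment-emergent", and its only condition is "whenever the portion of the date is consistent with that of the study treatment". Where the known part does not match, the fallback applies: "Otherwise, it will be imputed to the earliest date consistent with the partial date".
- **Wholly missing onset (section 8.11.1).** "A completely missing onset date will be imputed as the day of treatment". No condition is attached.
- **Stop date and duration (section 8.11.1).** "Partial stop dates will be assumed to be the latest possible day consistent with the partial date", and "AE duration will be calculated as (Stop Date – Start Date) + 1".
- **Use of the dates (section 8.11.1).** The main safety summary covers events within 28 days of any dose and compares the arms by risk differences with Miettinen-Nurminen intervals. A 7-day summary and by-dose frequencies are also planned.
- **Collection period (section 7.2).** Adverse events "will be collected for each subject from the time when informed consent is obtained through Week 88". Section 7.1.1 likewise counts events from the screening visit onwards.

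**The concern.** Imputing towards the dose is a sensible conservative choice while the event could have followed the dose. It stops being conservative once the record shows that the event was over before the dose was given. The rule as worded cannot tell these two situations apart, because it never consults the stop date.

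Two things follow. An event that cannot be emergent to a dose is counted as emergent to it, and its computed duration is zero or negative. At stake are the content of the 7-day and 28-day summaries for events before Dose 1, and the by-dose tables and durations for events between doses.

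**Working it through.** The protocol states no figure for this rule, so there is none to reproduce. The check applies the wording literally to illustrative dates.

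**General form.** If the onset is moved to the dose date and the stop is k days before the dose, then duration = (stop − dose) + 1 = 1 − k. This is 0 for k = 1 and negative for k ≥ 2.

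**Event before Dose 1.** Onset March 2018 (day unknown), stop 5 March, Day 0 on 26 March. The month matches, so the imputed onset is 26 March and the duration is (5 − 26) + 1 = −20 days. The event sits on the dose day, inside both windows.

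**More cases, with Dose 1 assumed on 20 June 2018:**

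| Recorded onset | Stop | Imputed onset | Duration (days) | Within 28 days of Dose 1? |
|---|---|---|---|---|
| Jun 2018 | 10 Jun | 20 Jun | −9 | yes |
| Jun 2018 | 18 Jun | 20 Jun | −1 | yes |
| Jun 2018 | 19 Jun | 20 Jun | 0 | yes |
| 2018 | 15 May | 20 Jun | −35 | yes |
| 2018 | May 2018, set to 31 May | 20 Jun | −19 | yes |
| missing | 25 Apr | 20 Jun | −55 | yes |
| May 2018 | 10 Jun | 1 May | 41 | no |
| Jun 2018 | Jun 2018, set to 30 Jun | 20 Jun | 11 | yes |

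The first six events ended before the dose and are misplaced. The last two are handled acceptably. In the final row the stop is not known to precede the dose, so keeping the event is defensible.

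**Event between doses.** Onset March 2018, stop 10 March, Dose 2 on 20 March. The rule gives onset 20 March and duration (10 − 20) + 1 = −9 days, credited to Dose 2. With Week 4 scheduled at 28 ± 4 days, Dose 1 fell between 16 and 24 February. The true onset lay between 1 and 10 March, which is 5 to 22 days after Dose 1. The event therefore belongs in the 28-day summary anyway; only its dose attribution and its duration are wrong.

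Doses 2 and 3 are nominally 56 days apart, so about 28 days of that interval lie outside the window that follows Dose 2. An event late in that interval that ended before Dose 3 could enter the 28-day summary wrongly.

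**Effect on the risk difference.** Suppose a fraction q of otherwise event-free subjects in each arm gains a spurious event of a given term. Each arm's risk p becomes p + q(1 − p), so the difference becomes (pV − pP)(1 − q). As an illustration only, take 10% against 0%, the whole-study sinusitis figures that section 2.3 reports from Phase 2b. With q assumed at 1%, the risks become 10.9% and 1.0%, a difference of 9.9 points instead of 10. At q = 0.5% it is 9.95 points, and at q = 2% it is 9.8.

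**The case against.** The case for leaving the rule alone has four parts.

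1. *Purpose.* The rule declares a conservative aim, and stop-date caps and the choice among doses are details that a statistical analysis plan commonly settles. That plan is not shown. This stands for the choice of dose. It does not stand for the stop date: the protocol states a complete rule, and a plan that capped it would depart from the protocol's wording.
2. *Few events.* Adverse events are queried at every visit and call, and diaries are kept for seven days after each dose, so incomplete onset dates should be uncommon. This stands, and it is the main reason the point is minor.
3. *Pre-dose conditions.* Section 7.1.1 says that conditions present before study drug count as adverse events only if they worsen afterwards. The same section, however, records events from screening onwards and lists complications of protocol procedures before dosing as adverse events. Resolved pre-dose events are therefore on file.
4. *No duration analysis.* Section 8 gives the duration formula but names no comparison that uses it. This stands: impossible durations would spoil listings and descriptive summaries, not a stated between-arm test.

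**Conclusion.** The point holds and is minor. Followed exactly, section 8.11.1 classes an event known to have ended before Dose 1 as treatment-emergent in the 7-day and 28-day summaries and gives it a duration of zero or less. Nothing elsewhere in the protocol corrects this. Between doses, the error usually concerns attribution and duration rather than entry into the main summary.

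The number of affected events cannot be estimated from the protocol. The slight shrinkage of the risk differences assumes that the arms gain spurious events at the same rate. That is reasonable for events before Dose 1, since randomization takes place on Day 0, but it is not guaranteed later.

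Three stronger readings are not supported.

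- A reader might infer that the main safety comparison is materially diluted. The planned measure is a risk difference, and it shrinks only by the factor 1 − q.
- A reader might estimate the share of events misdated from the 10-week screening window. That window runs from biopsy collection, which may precede consent, and the protocol gives no frequency of incomplete dates or of stops before the dose.
- A reader might extend the criticism to an event of unknown onset that is first reported late in follow-up. Without a stop date before the dose, placing it on the dose day is a defensible conservative choice.

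**What to change.** Replace the onset sentences in section 8.11.1 with wording such as the following, and keep the present fallback for partial dates that match no dose:

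> A partial or missing onset is imputed to the date of the earliest dose consistent with the known part of the date (Dose 1 if wholly missing), provided the stop date, after any imputation, is missing or ongoing, or falls on or after that dose. If the stop date precedes that dose, the onset is imputed to the earliest date consistent with the known part (or, if wholly missing, to the stop date), and the event is not counted as emergent to that dose. An imputed onset is never later than the stop date.

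Applied to the cases above:

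- March 2018 with stop 5 March (Day 0 on 26 March): starts 1 March, lasts 5 days, not emergent.
- June 2018 with stop 10 June: starts 1 June, lasts 10 days, not emergent.
- 2018 with stop 15 May: starts 1 January, lasts 135 days, not emergent.
- Missing with stop 25 April: starts and stops on 25 April, lasts 1 day, not emergent.
- The between-dose event with stop 10 March: starts 1 March, lasts 10 days, stays in the 28-day summary and is credited to Dose 1.

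Conservative imputation is kept wherever the event could have followed the dose. The cost is a few sentences and a small change to the derivation code, with no new data.

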8.13 PHYSICAL EXAMINATION

The percentage of subjects with abnormal physical examination findings at each time point will be summarized by treatment arm and by body system, for the ITT population.

8.14 PATIENT REPORTED OUTCOMES

As an exploratory endpoint, patient reported outcomes will be compared between treatment arms, based on PRO endpoints. Median changes from baseline for the SF-36 and EQ-5D-5L responses and median days of worsened quality of life for the Week 40 Quality of Life questionnaire will be analyzed using exact non-parametric 95% confidence intervals for the differences in medians. The proportion of subjects who report a worsened quality of life for the Week 40 Quality of Life questionnaire will be analyzed using a 95% Miettinen and Nurminen confidence interval for the difference in proportions.

In addition, the Week 36 and beyond outcomes will be summarized according to those with excision versus those without excision.

The mITT population will be used for PRO analyses.

8.15 MISSING VALUES

Missing data will be considered as non-regressors (failures) for the ITT efficacy analysis. A subject's regression outcome is missing if her CIN grade and HPV clearance at Week 36 cannot be determined. Also, any subject who undergoes an unscheduled excision or biopsy in which tissue sample was obtained after Dose 1 and before Week 36 will be considered a non-regressor regardless of the Week 36 result. Efficacy analyses using the mITT population will be conducted and will serve as sensitivity analyses regarding missing data.

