2.1 ENDPOINT ASSESSMENT

In the Phase 2b study, subjects were randomized 3:1 to the VGX-3100 frozen formulation arm or the Placebo arm. All subjects were scheduled to receive treatment on Day 0, Week 4 and Week 12 and undergo repeat cervical biopsy or surgical excision (i.e. LEEP, LLETZ, CKC) of the cervix at Week 36 to assess efficacy. The primary endpoint was histopathologic regression of cervical lesions to CIN1 or less at the Week 36 visit, and the secondary endpoint was clearance of HPV-16/18 in combination with histopathologic regression of cervical lesions to CIN1 or less.

The primary endpoint for the Phase 3 study is based upon the results of the Phase 2b study. Given that HPV persistence is an important factor in the clinical progression of dysplasia and also based upon the findings of the secondary objective of the Phase 2b study, the responder definition for the Phase 3 primary endpoint determination will take into consideration both histological regression of cervical HSIL and clearance of high-risk HPV-16/18.

The proportion of subjects who achieved this endpoint in the Phase 2b study was 35% (40%) of VGX-3100 subjects versus 14% (15%) for placebo, in an intention-to-treat analysis and modified intention-to-treat analysis, respectively. The composite endpoint of histologic regression and virologic clearance will be primary in the Phase 3 study, and histologic regression endpoint will be a secondary endpoint.

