8.2 RANDOMIZATION AND BLINDING

Subjects will be randomized (2 VGX-3100:1 Placebo) in a stratified manner according to a) the degree of CIN observed in the biopsy specimens at screening (CIN2 vs. CIN3), b) BMI category

(≤25 vs. >25 kg/m²) on Day 0, and c) age category (<25 years vs. ≥25 years) on Day 0. There will be no pre-determined number of subjects required to be randomized within each stratum. To ensure that milder CIN2 disease is not over-represented in the study, the percentage of subjects enrolled with CIN2 will not exceed 50% of the total enrolled. A group of sequential allocation numbers will be designated for use by each participating country.

The study is double-blinded.

8.3 SAMPLE SIZE/POWER

A sample of 198 subjects will be randomized to receive either 6 mg VGX-3100 or placebo IM followed by EP in a 2:1 ratio. This sample size provides 90% power to declare VGX-3100 superior to placebo, assuming the true proportion of subjects who achieve the primary endpoints is 35% and 14% for VGX-3100 and placebo, respectively. These proportions also incorporate missing data (~10%) classified as non-regressors (failures). The assumptions are based on the Phase 2 study results.

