8.9 EFFICACY ANALYSES

The true treatment effect on the primary endpoint is $\delta = p_V - p_P$, where p_V and p_P denote the true population probabilities of the primary endpoint for VGX-3100 and Placebo, respectively. The primary hypothesis of superiority is:

$$H_0$$
: $\delta \leq 0$ vs. H_1 : $\delta > 0$.

A p-value for this hypothesis test and corresponding 95% confidence interval will be computed based on the method of Miettinen and Nurminen [29]. Superiority will be concluded if the one-sided p-value is <0.025 and the corresponding lower bound of the 95% CI exceeds zero.

The secondary efficacy endpoints will be analyzed in the same manner as the primary hypothesis, but without the hypothesis test p-values.

The histopathologic efficacy time frame is defined by those who have undergone a biopsy or surgical excision at any time starting from 14 days prior to the protocol-specified target date of Week 36. It also includes subjects who undergo early excision or biopsy on or after Dose 1 but prior to this time frame or subjects who have no endpoint data for this time frame; these subjects are considered as failures for the efficacy endpoints. Table 7 through Table 11 provide details for the definition of the endpoint responses.

An exploratory analysis will examine the relationship between the primary efficacy endpoint and also the secondary efficacy endpoints of regression and clearance individually and the Immunoscore results. Relationships will be examined by using logistic regression models which model the efficacy outcomes versus the Immunoscore results and treatment group as regressor variables.

An exploratory analyses will examine the relationship between the primary efficacy endpoint and a) miRNA results, b) DNA methylation results, c) colposcopy results, d) cytology results, and e) HPV results. Relationships will be examined by using logistic regression models which model the primary endpoint outcome versus these results and treatment group as regressor variables.

Other exploratory analyses will examine durability of clearance of HPV-16 and/or HPV-18 infection from cervical tissue at Weeks 62 and 88. Descriptive statistics will be utilized; percentages of subjects who cleared will be presented by time point or anatomic location and treatment group.

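### The missing-data sensitivity analysis named in Section 8.15 is a complete-case analysis that never varies the missing women's outcomes by arm, so it says little about how a marginal positive result depends on them

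*Protocol*

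**What the plan says.** All references are to protocol version 5.0.

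- **Primary rule (Section 8.15).** A missing outcome counts as a failure in the ITT analysis.
- **Sensitivity analysis (Section 8.15).** "Efficacy analyses using the mITT population will be conducted and will serve as sensitivity analyses regarding missing data".
- **mITT set (Section 8.4).** It contains women who received at least one dose and who have the endpoint being analysed, grouped as randomized. It is therefore a complete-case set, and the section calls its analysis supportive. The per-protocol set also requires the endpoint, so it adds no different assumption about missing outcomes.
- **Expected missingness (Section 8.3).** "These proportions also incorporate missing data (~10%) classified as non-regressors (failures"). No split by arm is given.
- **Phase 2b result on the same composite (Section 2.1).** "35% (40%) of VGX-3100 subjects versus 14% (15%) for placebo", the first figure in each pair being ITT and the bracketed one mITT.
- **Decision rule (Section 8.9).** "Superiority will be concluded if the one-sided p-value is <0.025", by the Miettinen-Nurminen method, with the lower confidence bound above zero.

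**The concern.** A missing-data sensitivity analysis should change the assumption about the unobserved outcomes and show whether the conclusion survives. Moving from ITT to mITT removes the missing women from the denominators and leaves the responder counts alone. If the missing fraction is similar in both arms, both rates are divided by nearly the same factor, the difference and its standard error grow together, and the test statistic hardly moves.

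Missing-as-failure is conservative for each arm's own rate but not necessarily for the difference: a missing placebo woman who had in fact responded enlarges the apparent effect when scored as a failure. Section 1.1.4 itself notes that spontaneous regression occurs in this disease, so such women are possible. Neither planned analysis considers them. What is at stake is a result close to 0.025 being reported as supported by a sensitivity analysis that did not examine the scenario most able to overturn it.

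**Working it through.** **Inputs.** 198 women randomized 2:1 (Sections 8.2 and 8.3), so 132 on VGX-3100 and 66 on placebo; planned rates 35% and 14%; one-sided 0.025 (Section 8.9). About 10% of 198 is 20 missing women. Their split by arm is not stated, so every split below is an assumption.

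**The plan's own figure.** The normal approximation with 132 v 66, 35% v 14% and one-sided 0.025 gives power of 90.3%. Exact enumeration of the Miettinen-Nurminen test gives 90.8%. The stated 90% reproduces.

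**Formula.** At a null difference of zero, with pooled rate p = (x1 + x2)/N and N = n1 + n2, the statistic is

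z = (x1/n1 − x2/n2) / √[ p(1 − p)(1/n1 + 1/n2) · N/(N − 1) ].

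ITT uses n = 132 and 66. mITT uses the same responder counts with the missing women taken out of n.

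**Step 1: missingness about equal (13/7, or 9.8% v 10.6%).** Take 35 v 9 responders, the smallest significant result with 9 placebo responders.
- ITT: 35/132 − 9/66 = 0.1288; standard error 0.0628; z = 2.05; p = 0.0202.
- mITT: 35/119 − 9/59 = 0.1416; standard error 0.0689; z = 2.06; p = 0.0199.

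The difference and the standard error both rise by about 10%, so the p-value stays put. Over all possible responder counts with 13/7 missing, 2,677 results are significant under ITT. mITT reverses one of them (21 v 4: 0.0249 becomes 0.0251).

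**Step 2: more missing on VGX-3100.** If ITT rate = mITT rate × (1 − missing fraction), the Phase 2b figures imply 1 − 35/40 = 12.5% missing on VGX-3100 and 1 − 14/15 = 6.7% on placebo. These come from rounded percentages. A similar split here is 16/4.
- 35 v 9: 35/116 v 9/62, p = 0.0107 (ITT 0.0202).
- 38 v 11: ITT p = 0.0316, not significant; mITT (38/116 v 11/62) p = 0.0165.

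Of the 2,519 ITT-significant results possible with this split, mITT reverses none.

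**Step 3: proportionally more missing on placebo.**
- 35 v 9 with 11/9 missing (8.3% v 13.6%): 35/121 v 9/57, p = 0.0294.
- 35 v 9 with 10/10 missing: 35/122 v 9/56, p = 0.0354.

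Here mITT does challenge the primary result. It responds to how many women are missing in each arm, not to what their outcomes were.

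**Step 4: vary the missing placebo outcomes (132 v 66, missing VGX-3100 women kept as failures).**

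| Observed responders | Missing placebo women counted as responders | p |
|---|---|---|
| 35 v 9 | 0 | 0.0202 |
| 35 v 9 | 1 | 0.0364 |
| 46 v 9 (planned rates) | 0 | 0.0009 |
| 46 v 9 | 5 | 0.0248 |
| 46 v 9 | 6 | 0.0412 |

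**Step 5: let both arms move.** From 35 v 9, counting 2 of the 13 missing VGX-3100 women and 1 of the 7 missing placebo women as responders gives 37/132 v 10/66, p = 0.0226, still significant. With 4 of the 13, three placebo women are needed to lose it (39 v 11: 0.0249; 39 v 12: 0.0428).

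**The case against.** **This is detail for the SAP.** Only the protocol is at hand, and a SAP may add other missing-data analyses. That stands against any claim that mITT is the trial's only such analysis. It does not remove the point: Section 8.15 itself gives mITT this role, so this is a stated choice of method and not a gap.

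**mITT is not inert.** A reader might infer from Step 1 that mITT cannot reveal dependence on the missing women, or could never disagree with ITT. The documents do not support that. Balance between arms is an assumption; Section 8.3 gives only an overall figure. Shifting two women in the example, from 13/7 to 11/9, takes mITT across 0.025. The estimate also changes under balance: at 46 v 9 with 13/7 missing, the difference goes from 21.2 to 23.4 points.

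**Phase 2b points the other way.** A reader might take the unequal Phase 2b missingness as evidence that missing-as-failure flatters VGX-3100. It is not. More women were missing on VGX-3100, and the difference was 35 − 14 = 21 points under ITT against 40 − 15 = 25 under mITT, so the primary rule shrank the difference there. Those figures show only the direction in which mITT would move.

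**The one-woman example is one-sided and near the threshold.** This stands. Any result at p = 0.020 is fragile, and Step 5 shows that similar response fractions among the missing in both arms leave it significant. An arm-by-arm table would show which situation applies.

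**Conclusion.** The concern holds in a limited form. The sensitivity analysis that Section 8.15 names is complete-case and does not vary the missing women's outcomes by arm. With missingness about equal it nearly duplicates the primary test, reversing 1 of 2,677 significant results at 13/7. With a Phase 2b-like split it is more favourable than ITT and reverses none of 2,519. It challenges a positive result only when placebo loses proportionally more women.

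The practical weight falls on marginal results: one responder among the missing placebo women is enough at 35 v 9, while six of seven are needed at the planned effect, which is therefore robust. These tipping points assume that no missing VGX-3100 woman responded, and all missing counts by arm are assumptions around the stated 10% or so. The primary analysis and the sample size are not in question.

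**What to change.** Keep ITT with missing as failure as the primary analysis, and keep mITT as supportive, which is how Section 8.4 already describes it. In Section 8.15, replace mITT as the named missing-data sensitivity analysis with an arm-specific tipping-point table for the primary endpoint. The table gives the Miettinen-Nurminen p-value for every number of missing women counted as responders in each arm and marks where significance is lost. With 13 and 7 missing that is 14 × 8 = 112 cells.

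The cost is one extra table from data already collected, with no change to the primary test or sample size. The downside is that a marginal result may look more fragile.
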